8.2 DATA QUALITY ASSURANCE

A risk-based approach is used for trial quality management. It is initiated by the assessment of critical data and processes for trial subject protection and reliability of the results as well as identification and assessment of associated risks. An Integrated Quality and Risk Management Plan documents the rationale and strategies for risk management during trial conduct including monitoring approaches, vendor management and other processes focusing on areas of greatest risk.

Continuous risk review and assessment may lead to adjustments in trial conduct, trial design or monitoring approaches.

A quality assurance audit/inspection of this trial may be conducted by the sponsor, sponsor's designees, or by IRB / IEC or by regulatory authorities. The quality assurance auditor will have access to all medical records, the investigator's trial-related files and correspondence, and the informed consent documentation of this clinical trial.

8.3 RECORDS

CRFs for individual subjects will be provided by the sponsor. For drug accountability, refer to Section [4.1.8](#).

[REDACTED]
In the [REDACTED] – the validated [REDACTED] system is used for processing information and controlling data collected in clinical studies. In addition to its function as a procedure control system, [REDACTED] serves as database. Instead of being entered into CRFs, selected data are directly entered into the [REDACTED] system.

8.3.1 Source documents

In accordance with regulatory requirements, the investigator should prepare and maintain adequate and accurate source documents and trial records for each trial subject that include all observations and other data pertinent to the investigation. Source data as well as reported data should follow the 'ALCOA principles' and be atttributable, legible, contemporaneous, original, and accurate. Changes to the data should be traceable (audit trail).

Data reported on the CRF must be consistent with the source data or the discrepancies must be explained.

Before providing any copy of subjects' source documents to the sponsor, the investigator must ensure that all subject identifiers (e.g., subject's name, initials, address, phone number,

and social security number) have properly been removed or redacted to ensure subject confidentiality.

If the subject is not compliant with the protocol, any corrective action (e.g. re-training) must be documented in the subject file.

For the CRF, data must be derived from source documents, for example:

- Subject identification: sex, year of birth (in accordance with local laws and regulations)
- Subject participation in the trial (substance, trial number, subject number, date subject was informed)
- Dates of subject's visits, including dispensing of trial medication
- Medical history (including trial indication and concomitant diseases, if applicable)
- Medication history
- AEs and outcome events (onset date [mandatory], and end date [if available])
- SAEs (onset date [mandatory], and end date [if available])
- Concomitant therapy (start date, changes)
- Originals or copies of laboratory results and other imaging or testing results, with proper documented medical evaluation (in validated electronic format, if available)
- ECG results (original or copies of printouts)
- Completion of subject's participation in the trial (end date; in case of premature discontinuation, document the reason for it, if known)
- Prior to allocation of a subject to a treatment into a clinical trial, there must be documented evidence in the source data (e.g. medical records) that the trial participant meets all inclusion criteria and does not meet any exclusion criteria. The absence of records (either medical records, verbal documented feedback of the subject or testing conducted specific for a protocol) to support inclusion/exclusion criteria does not make the subject eligible for the clinical trial.

Data directly entered into ClinBase™ (that is, without prior written or electronic record) are considered to be source data. The place where data are entered first will be defined in a trial specific Source Data Agreement. The data in ClinBase™ are available for inspection at any time.

8.3.2 Direct access to source data and documents

The investigator /institution will allow site trial-related monitoring, audits, IRB / IEC review and regulatory inspections. Direct access must be provided to the CRF and all source documents/data, including progress notes, copies of laboratory and medical test results, which must be available at all times for review by the Clinical Research Associate, auditor and regulatory inspector (e.g. FDA). They may review all CRFs and informed consents. The accuracy of the data will be verified by direct comparison with the source documents described in Section [8.3.1](#). The sponsor will also monitor compliance with the protocol and GCP.

8.3.3 Storage period of records

Trial site:

The trial site(s) must retain the source and essential documents (including ISF) according to the local requirements valid at the time of the end of the trial.

Sponsor:

The sponsor must retain the essential documents according to the sponsor's SOPs.

8.4 EXPEDITED REPORTING OF ADVERSE EVENTS

BI is responsible to fulfil their legal and regulatory reporting obligation in accordance with regulatory requirements.

8.5 STATEMENT OF CONFIDENTIALITY AND SUBJECT PRIVACY

Individual subject data obtained as a result of this trial is considered confidential and disclosure to third parties is prohibited with the exceptions noted in Section [8.7](#).

Data protection and data security measures are implemented for the collection, storage and processing of patient data in accordance with the principles 6 and 12 of the WHO GCP handbook.

Personalised treatment data may be given to the subject's personal physician or to other appropriate medical personnel responsible for the subject's welfare. Data generated at the site as a result of the trial need to be available for inspection on request by the participating physicians, the sponsor's representatives, by the IRB / IEC and the regulatory authorities.

8.5.1 Collection, storage and future use of biological samples and corresponding data

Measures are in place to comply with the applicable rules for the collection, storage and future use of biological samples and clinical data, in particular

- Sample and data usage has to be in accordance with the informed consent
- The BI-internal facilities storing biological samples from clinical trial participants as well as the external storage facility are qualified for the storage of biological samples collected in clinical trials.
- An appropriate sample and data management system, incl. audit trail for clinical data and samples to identify and destroy such samples according to ICF is in place
- A fit for the purpose documentation (biomarker proposal, analysis plan and report) ensures compliant usage
- A fit for purpose approach will be used for assay/equipment validation depending on the intended use of the biomarker data

Samples and/or data may be transferred to third parties and other countries as specified in the ICF.

8.6 TRIAL MILESTONES

The start of the trial is defined as the date when the first subject in the whole trial signs informed consent.

The end of the trial is defined as the date of the last visit of the last subject in the whole trial ('Last Subject Completed').

Early termination of the trial is defined as the premature termination of the trial due to any reason before the end of the trial as specified in this protocol.

Temporary halt of the trial is defined as any unplanned interruption of the trial by the sponsor with the intention to resume it.

Suspension of the trial is defined as an interruption of the trial based on a Health Authority request.

The EC/competent authority in each participating EU member state will be notified about the trial milestones according to the laws of each member state.

A final report of the clinical trial data will be written only after all subjects have completed the trial in all countries (EU or non-EU), so that all data can be incorporated and considered in the report.

The sponsor will submit to the EU database a summary of the final trial results within one year from the end of a clinical trial as a whole, regardless of the country of the last patient (EU or non-EU).

8.7 ADMINISTRATIVE STRUCTURE OF THE TRIAL

The trial is sponsored by Boehringer Ingelheim (BI).

The trial will be conducted at the [REDACTED] under the supervision of the Principal Investigator. Relevant documentation on the participating (Principal) Investigators (e.g. their curricula vitae) will be filed in the ISF.

BI has appointed a Clinical Trial Leader, responsible for coordinating all required trial activities, in order to

- Manage the trial in accordance with applicable regulations and internal SOPs
- Direct the clinical trial team in the preparation, conduct, and reporting of the trial
- ensure appropriate training and information of Clinical Trial Manager, Clinical Research Associates, and investigators of the participating trial site

The trial medication (BI 425809) will be provided by the [REDACTED]. Fluconazole (Diflucan[®]) will be purchased by the clinical site at a public pharmacy.

Safety laboratory tests will be performed by the local laboratory of the trial site ([REDACTED]).

Analyses of BI 425809 concentrations in plasma will be performed at [REDACTED]
[REDACTED]. Analyses of fluconazole concentrations in plasma will be performed at [REDACTED]
[REDACTED]

On-site monitoring will be performed by BI or a contract research organisation appointed by BI.

Data management and statistical evaluation will be done by BI according to BI SOPs.

Tasks and functions assigned in order to organise, manage, and evaluate the trial are defined according to BI SOPs. A list of responsible persons and relevant local information can be found in the ISF.

10. APPENDICES

Not applicable.

[figure not shown]

[figure not shown]

## 2. LIST OF ABBREVIATIONS

Term	Definition / description
AE	Adverse Event
AESI	Adverse event of special interest
ALT	Alanine aminotransferase
AST	Aspartate aminotransferase
AUC 0-215h	Area under the concentration-time curve of the analyte in plasma over the time interval from 0 to 215 hours post administration of BI 425809
AUC 0-∞	Area under the concentration-time curve of the analyte in plasma over the time interval from 0 extrapolated to infinity
BI	Boehringer Ingelheim
C max	Maximum measured concentration of the analyte in plasma
COVID	Coronavirus disease
CTP	Clinical Trial Protocol
CTR	Clinical Trial Report
CV	Arithmetic coefficient of variation
ECG	Electrocardiogram
gCV	geometric coefficient of variation
gMean	Geometric mean
ICH	International Conference On Harmonisation
iPD	Important protocol deviations
LLOQ	Lower limit of quantification
MedDRA	Medical Dictionary For Regulatory Activities
PK	Pharmacokinetics
PKS	Pharmacokinetic parameter analysis set
PR	Pulse rate
RAGe	Report appendix generator
REP	Residual effect period
RPM	Report Planning Meeting
SAE	Serious adverse event
SD	Standard Deviation
SOC	System Organ Class

Term	Definition / description
TS	Treated set
TSAP	Trial Statistical Analysis Plan
ULN	Upper limit of normal range

### **3. INTRODUCTION**

As per ICH E9 (1) the purpose of this document is to provide a more technical and detailed elaboration of the principal features of the analysis described in the revised CTP, and to include detailed procedures for executing the statistical analysis of the primary variables and other data.

This TSAP assumes familiarity with the CTP. In particular, the TSAP is based on the planned analysis specification as written in CTP Section 7 "Statistical Methods and Determination of Sample Size". Therefore, TSAP readers may consult the CTP for more background information on the study, e.g., on study objectives, study design and population, treatments, definition of measurements and variables, planning of sample size, randomisation.

Study data as collected in the eCRF will be stored in a trial database within the RAVE EDC system. All study data also including external data will then be uploaded to the CDR data warehouse.

The statistical analyses will be performed within the validated working environment CARE, including SASTM (current Version 9.4, by [REDACTED]), and a number of SASTM-based tools (e.g., macros for the analyses of AE data or laboratory data; Report Appendix Generator system (RAGe) for compilation/formatting of the CTR appendices).

PK parameters will be calculated using Phoenix WinNonlinTM software (version Phoenix 6.3, [REDACTED]).

#### **4. CHANGES IN THE PLANNED ANALYSIS OF THE STUDY**

All analyses described in this TSAP are in accordance with the statistical methods described in the CTP.

## **5. ENDPOINTS**

### **5.1 PRIMARY ENDPOINT**

Primary endpoints are the following PK endpoints of BI 425809 as defined in Section 2.1.2 of the CTP:

- $AUC_{0-215h}$  (area under the concentration-time curve of the analyte in plasma over the time interval from 0 to 215 hours post administration of BI 425809)
- $C_{max}$  (maximum measured concentration of the analyte in plasma)

### **5.2 SECONDARY ENDPOINTS**

[figure not shown]
#### **5.2.1 Key secondary endpoints**

[figure not shown]
Not applicable.

#### **5.2.2 Secondary endpoint**

Secondary endpoint is the following PK endpoint of BI 425809 as defined in Section 2.1.3 of the CTP.

- $AUC_{0-\infty}$  (area under the concentration-time curve of the analyte in plasma over the time interval from 0 extrapolated to infinity)

## **6. GENERAL ANALYSIS DEFINITIONS**

### **6.1 TREATMENTS**

For basic study information on the treatment to be administered, and selection of dose, cf. Section 4 of the CTP.

Subjects will receive the following two treatments in a fixed sequence (reference treatment always followed by test treatment).

In Period Reference R, all subjects will receive 1 tablet containing

- 10 mg BI 425809 (Reference Treatment R) as a single dose

Afterwards, in Period Test T, all subjects will receive

- 2 capsules, each containing 200 mg Fluconazole, once daily for 13 days (Day -4 to Day 9) and 1 tablet containing 10 mg BI 425809 as a single dose on Day 1 (Test Treatment T).

For statistical analysis of AEs, the following analysis phases are defined for each subject.

Table 6.1: 1 Analysis phases for statistical analysis of AEs, and actual treatment for analysis of laboratory data and vital signs

Study analysis phase	Label	Start	End
Screening 	Screening	Date of informed consent	Date/time of first administration of BI 425809
On treatment	BI 425809	Date/time of first administration of BI 425809	Date/time of first administration of BI 425809 + REP (11 days) or 12:00 a.m. on day after last contact date (whichever occurs first)
Follow-up	F/U BI 425809	Date/time of first administration of BI 425809 + REP (11 days)	Date/time of first administration of Fluconazole or 12:00 a.m. on day after last contact date (whichever occurs first)
On treatment	Fluconazole	Date/time of first administration of Fluconazole	Date/time of second administration of BI 425809 or 12:00 a.m. on day after last contact date (whichever occurs first)
On treatment	BI + Fluconazole	Date/time of second administration of BI 425809	Date/time of second administration of BI 425809 + REP (14 days) or 12:00 a.m. on day after last contact date (whichever occurs first)
Follow-up	F/U BI + Fluconazole	Date/time of second administration of BI 425809 + REP (14 days)	12:00 a.m. on day after last contact date

 See [Section 6.7](#) for definition of baseline, which will be used in the statistical analyses of safety laboratory data and vital signs.

The on-treatment phase for 'BI + Fluconazole' includes both the REP for BI 425809 (14 days) and Fluconazole (6 days). Since the second administration of BI 425809 is scheduled at 9:00 am on Visit 3, Day 1, while the last administration of Fluconazole is scheduled at 8:00 am on the Visit 3, Day 9 (see CTP, Flow chart). Therefore, Date/time of the second administration of BI 425809 + REP (14 days) is one hour after Date/time of the last administration of Fluconazole + REP (6 days).

AE summary tables will present results for the on-treatment phases only. All AEs will be listed.

In AE tables in CTR Section 15.3 (but not in Appendix 16.1.13.1.8.1 and Appendix 16.1.13.1.8.2 AE tables), the following totals will be provided in addition:

- **"Total BI"**, defined as the total over all on-treatment phases involving BI 425809
- **"Total Fluconazole"**, defined as the total over all on-treatment phases involving Fluconazole
- **"Total on-trt"**, defined as the total over all on-treatment phases

Safety laboratory data, vital signs and PK parameters will be analyzed based on treatment periods (BI 425809 and BI+Fluconazole) with clear differentiation between baseline (cf. [Section 6.7](#)) and post-baseline measurements. Measurements will be considered on-treatment, if they were taken within the on-treatment phases of BI 425809 or BI+Fluconazole as defined in [Table 6.1: 1](#). More details on the technical implementation of these analyses are provided in the ADS Plan of this TSAP.

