3.3.4.1 Discontinuation of trial treatment

An individual subject will discontinue trial treatment if:

1. The subject wants to discontinue trial treatment, without the need to justify the decision
2. The subject has repeatedly shown to be non-compliant with important trial procedures and, in the opinion of both, the investigator and sponsor representative, is not willing or able to adhere to the trial requirements in the future.
3. The subject needs to take concomitant medication that interferes with the investigational medicinal product or other trial treatment
4. The subject can no longer receive trial treatment for medical reasons (such as surgery, adverse events [AEs], or diseases)
5. The subject has an elevation of AST and/or ALT ≥ 3 -fold ULN
6. The subject has an elevation of AST and/or ALT ≥ 1.5 -fold ULN and a control blood sample, which will be withdrawn on the next day, confirms further meaningful increase of the respective parameter. It is with the investigator to evaluate the clinical significance of this increase taking into account its occurrence in relation to the 13 days of fluconazole treatment
7. The subject has an elevation of AST and/or ALT ≥ 3 -fold ULN and an elevation of total bilirubin ≥ 2 -fold ULN (measured in the same blood sample) and/or needs to be followed up according to the DILI checklist provided in the ISF
8. In case a rash occurs during the fluconazole dosing phase which is attributable to fluconazole treatment, the respective subject will discontinue study treatment

In addition to these criteria, the investigator may discontinue subjects at any time based on his or her clinical judgment.

Even if the trial treatment is discontinued, the subject remains in the trial and, given his/her agreement, will undergo the procedures for early treatment discontinuation and follow up as outlined in the [Flow Chart](#) and Section [6.2.3](#).

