6. INVESTIGATIONAL PLAN

6.1 VISIT SCHEDULE

Exact times of measurements outside the permitted time windows will be documented. The acceptable time windows for screening and the end of trial examination are provided in the [Flow Chart](#).

Study measurements and assessments scheduled to occur 'before' BI 425809 administration on Day 1 are to be performed and completed within a 3 h-period prior administration of BI 425809.

In ambulatory visits prior to administration of BI 425809 in period 2, the acceptable deviation from the scheduled time for ECG and laboratory tests will be -15 min.

Following administration of BI 425809, the acceptable deviation from the scheduled time for vital signs, ECG, and laboratory tests will be ± 45 min until Day 6. From Day 8 onwards, a deviation from the scheduled time for fluconazole administration, safety laboratory tests, and ECG of ± 60 min is acceptable.

If scheduled in the Flow Chart at the same time as a meal, blood sampling, vital signs, and 12-lead ECG recordings have to be done first. 12-lead ECG measurements should always be the first procedure. Furthermore, if several measurements including venepuncture are scheduled for the same time, venepuncture should be the last of the measurements due to its inconvenience to the subject and possible influence on physiological parameters.

For planned blood sampling times, refer to the Flow Chart. While these nominal times should be adhered to as closely as possible, the actual sampling times will be recorded and used for the determination of pharmacokinetic parameters.

If a subject misses an appointment, it will be rescheduled if possible. The relevance of measurements outside the permitted time windows will be assessed no later than at the Report Planning Meeting.

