7.3.4 Safety analyses

Safety will be analysed based on the assessments described in Section 2.2.2.2. All treated subjects (TS, refer to Section [7.2](#)) will be included in the safety analysis. Safety analyses will be descriptive in nature and based on BI standards. No hypothesis testing is planned.

For all analyses, the treatment actually administered (= treatment at onset) to the subject will be used (any deviations from the randomised treatment will be discussed in the minutes of the Report Planning Meeting).

Treatments will be compared in a descriptive way. Tabulations of frequencies/proportions will be used to evaluate categorical (qualitative) data, and tabulations of descriptive statistics will be used to analyse continuous (quantitative) data.

Measurements (such as ECG, vital signs, or laboratory parameters) or AEs will be assigned to treatments (see Section [4.1](#)) based on the actual treatment at the planned time of the measurement or on the recorded time of AE onset (concept of treatment emergent AEs). Therefore, measurements planned or AEs recorded prior to first intake of trial medication will be assigned to the screening period, those between first trial medication intake and end of REP (see Section [1.2.3](#)) will be assigned to the treatment period. Events occurring after the REP but prior to next intake or end of trial termination date will be assigned to 'follow-up'. In case of two or more treatments, the follow-up will be summarized according to the previous treatment. These assignments including the corresponding time intervals will be defined in detail in the TSAP. Note that AEs occurring after the last per protocol contact but entered before final database lock will be reported to Pharmacovigilance only and will not be captured in the trial database.

Additionally, further treatment intervals (analysing treatments) may be defined in the TSAP in order to provide summary statistics for time intervals, such as combined treatments, on-treatment totals, or periods without treatment effects (such as screening and follow-up intervals).

Adverse events will be coded using the Medical Dictionary for Regulatory Activities (MedDRA). Frequency, severity, and causal relationship of AEs will be tabulated by treatment, system organ class, and preferred term. SAEs, AESIs (see Section [5.2.5.1.4](#)), and other significant AEs (according to ICH E3) will be listed separately.

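### The SAP's 'Fluconazole' adverse-event phase has no residual-effect end and no follow-up phase for a subject who stops before the second BI 425809 dose

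*SAP*

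**What the plan says.** Protocol 7.3.4 sets the general rule. Events "those between first trial medication intake and end of REP (see Section" 1.2.3) belong to the treatment period. It continues: "Events occurring after the REP but prior to next intake or end of trial termination date will be assigned to" follow-up. The detailed intervals are left to the SAP.

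SAP Table 6.1: 1 implements this with three on-treatment rows. 'BI 425809' ends at the first dose plus an 11-day REP. 'BI + Fluconazole' ends at the second dose plus a 14-day REP. Both are capped at last contact. The row between them, 'Fluconazole', ends at "Date/time of second administration of BI 425809 or 12:00 a.m. on day after last contact date (whichever occurs first", with no REP term. The only follow-up row after fluconazole has started begins at "Date/time of second administration of BI 425809 + REP (14 days").

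The text below the table says the combined phase "includes both the REP for BI 425809 (14 days) and Fluconazole (6 days"). It supports this by noting that "the last administration of Fluconazole is scheduled at 8:00 am on the Visit 3, Day 9", so that the BI 425809 limit falls one hour after the fluconazole limit. SAP 6.1 also says that AE summary tables show on-treatment phases only and that all AEs are listed. SAP Section 4 declares every analysis to be in accordance with the protocol.

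On early stopping, Protocol 3.3.4.1 says: "Even if the trial treatment is discontinued, the subject remains in the trial".

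**The concern.** The table works for a subject who takes every dose. It has no correct end for a subject who starts fluconazole and never takes the second BI 425809 dose. For that subject the 'Fluconazole' phase runs to last contact, and the follow-up row cannot start because its anchor does not exist.

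Stopping at that stage is foreseeable. Four fluconazole doses precede Day 1 of the test period, and a liver panel (safety lab C) is drawn on Day -1. Protocol 3.3.4.1 lists liver-enzyme criteria, attributable rash and the subject's own wish as reasons to stop. Contact after the REP is foreseeable too: Protocol 3.3.4 asks that a discontinued subject be questioned, if possible, at or after its end.

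At stake is which adverse events enter the descriptive tables. An early stopper's event after the REP would be tabulated under 'Fluconazole', 'Total Fluconazole' and 'Total on-trt'. A completer's event after the REP is follow-up and is left out. One subject in 15 is 6.7%, which exceeds the 5% incidence threshold that SAP 7.8.1 uses for registry disclosure of non-serious events, so one misassigned event could bring a preferred term over it.

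**Working it through.** **Clock.** Hours from the second BI 425809 dose, with Day 1, 09:00 = 0 and no Day 0. Fluconazole times from the protocol Flow Chart are -97, -73, -49 and -25 h (Days -4 to -1), -1 h (Day 1) and 191 h (Day 9). The REPs in the test period, from SAP 6.1, are 14 days (336 h) for BI 425809 and 6 days (144 h) for fluconazole.

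**1. The SAP's own figure.** BI 425809 limit: 0 + 336 = 336 h. Fluconazole limit: 191 + 144 = 335 h. The difference is 1 h, as stated. The figure is right, but it uses the scheduled Day 9 dose and so assumes full dosing.

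**2. A subject who stops before the second BI 425809 dose.** The REP ends at (last fluconazole dose) + 144 h. The SAP phase ends at midnight after last contact on Day c, which is 24c - 9 h: 375 h for Day 16 and 711 h for Day 30. Excess = (SAP end - REP end) / 24.

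| Last fluconazole dose | REP ends | Excess, last contact Day 16 | Excess, last contact Day 30 |
|---|---|---|---|
| Day -4 (-97 h) | 47 h, Day 3, 08:00 | (375 - 47)/24 = 13.7 d | (711 - 47)/24 = 27.7 d |
| Day -3 (-73 h) | 71 h, Day 4, 08:00 | 12.7 d | 26.7 d |
| Day -2 (-49 h) | 95 h, Day 5, 08:00 | 11.7 d | 25.7 d |
| Day -1 (-25 h) | 119 h, Day 6, 08:00 | (375 - 119)/24 = 10.7 d | (711 - 119)/24 = 24.7 d |

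If the Day 1 fluconazole dose is taken but BI 425809 is not, the REP ends at 143 h (Day 7, 08:00) and the excess is 9.7 to 23.7 d.

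**3. Earlier last contact.** If last contact is on the day the REP ends, the phase runs from 08:00 to midnight too long, which is 16 h. If last contact is on an earlier day, the last-contact cap applies first and the excess is zero.

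**4. Weight of one subject.** 1/15 = 6.7 percentage points in a row of the table, taking 15 subjects as the denominator.

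**5. The other end, 'BI + Fluconazole'.** This phase cuts into the fluconazole REP only if the last fluconazole dose comes more than 336 - 144 = 192 h (8 days) after the second BI 425809 dose. A Day 9 dose at the +60 min limit in Protocol 6.1 is at 191 + 1 = 192 h. Its REP then ends at 192 + 144 = 336 h, exactly at the phase end, so nothing is lost within tolerance. A dose 24 h late would lose 23 h.

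**The case against.** The strongest reply is that Protocol 7.3.4 delegates the exact intervals to the SAP, and that the protocol's REP section (1.2.3) is redacted, so the 6 days is known only from the SAP. That stands as a limit on the evidence. But permission to define intervals in detail does not cover dropping the REP for one drug when the governing rule is REP first, then follow-up, and when the SAP itself gives that drug a REP.

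A second reply is that the effect may be small or absent. Protocol 3.3.4 calls for an end-of-trial examination at discontinuation if possible, and Protocol 6.2.3 sends early discontinuers to the end-of-trial visit. Last contact may therefore come well before Day 16. This stands: the multi-day excess is a scenario, not an expectation.

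Third, the error adds events to the tables and does not hide any, all AEs are listed, and safety is descriptive. This also stands, and it limits the importance of the point.

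A reader might also infer more than the documents support:

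- **That the 60-minute dosing tolerance cuts the REP at the end of the combined phase.** It does not when BI 425809 is given on time (step 5). Protocol 6.1 does say "If a subject misses an appointment, it will be rescheduled if possible", but a last dose late enough to matter lies outside the tolerance, and SAP 6.2 takes dosing deviations to the Report Planning Meeting.
- **That any early stop of fluconazole is misassigned.** A subject who takes the second BI 425809 dose is governed by the 14-day REP and is assigned correctly.
- **That completers and early stoppers are defined differently within the 'Fluconazole' column.** A completer's 'Fluconazole' phase closes at the second BI 425809 dose and later events carry other labels, so the contrast after the REP applies to the total columns.
- **That each affected subject adds 6.7 points to the overall AE rate.** SAP 7.8.1 counts subjects, so someone who stopped because of an AE is already in the any-AE row. The 6.7 points is a ceiling, for a new row such as a preferred term.

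**Conclusion.** The point holds for one defined case: a subject who stops between the first fluconazole dose and the second BI 425809 dose and whose last contact falls on or after the day the 6-day REP ends. As written, the SAP keeps that subject on treatment to midnight after last contact, against the rule in Protocol 7.3.4 and its own REP, and Section 4 does not declare it.

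The excess ranges from zero to about 27.7 days, depending on the day of the last dose and of last contact. The upper part of that range assumes last contact at a Day 16 to 30 visit. The documents give no basis for the number of subjects affected, and it may be zero. The effect is confined to descriptive AE tables. It is a small but definite error in a stated rule, worth correcting before any such case has to be settled with the data in view.

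**What to change.** In SAP Table 6.1: 1:

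1. End 'Fluconazole' at the earliest of the second BI 425809 dose, the actual last fluconazole dose + REP (6 days), and midnight after last contact.
2. Add a row 'F/U Fluconazole' for subjects without a second BI 425809 dose, from that REP end to midnight after last contact.

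Optional and minor: end 'BI + Fluconazole' at the later of the second BI 425809 dose + 14 days and the actual last fluconazole dose + 6 days, capped at last contact, and start its follow-up row at the same point. This matters only for a last fluconazole dose more than 8 days after the second BI 425809 dose.

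The cost is one changed cell and one new row (two more cells for the optional part), with the matching phase derivation in the ADS plan. No new data should be needed, since all dosing is supervised at the site (Protocol 4.3) and use by each subject is recorded (Protocol 4.1.8).
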